We chose 2 and 5 weeks for the post-TKA assessments. Broadly speaking, we chose to study the 1st 5 wk post-TKA because this represents an important gap in rehabilitative care, as detailed above in the *Purpose and Objectives* section. Moreover, large structural and functional skeletal muscle changes occur, making it an optimal time to intervene with preventive modalities, such as NMES. The 2 wk time point was chosen in response to reviewer's requests for evaluation of additional potential mechanisms underlying atrophy and contractile dysfunction because this is the absolute closest point to the TKA surgery that our surgeons would allow muscle biopsies to be performed because patients are typically on anti-coagulant therapy for the first ~7-10 d post-TKA, a contraindication for muscle biopsy. The fact that our preliminary data suggests that atrophy is continual throughout the 5 wk time period argues that mechanisms contributing to atrophy and dysfunction are likely operative at the 2 wk time point.

We chose to focus on knee extensors because we and others have shown that they experience the

greatest functional decline (-42 to -60%;(6, 7)), 2- to ~3-fold greater than dorsi/plantarflexors (6), with atrophy of comparable magnitude to functional deficits. Moreover, the greatest functional declines occur in activities of daily living (ADL) with strong reliance on the extensor mechanism (eg, SCT, TUG; (3)), making knee extensor function an important determinant of TKA-related disability. Knowledge of the adaptations to TKA in all lower extremity muscles, as well as their response to NMES, is needed, but in lieu of practical limitations in studying this population (eg, # of muscles studied/biopsied) and available technologies for NMES, we have focused on the knee extensors because of their profound impact on physical function.

Literature cited:

1. Anonymous. (2009) Prevalence and most common causes of disability among adults--United States, 2005. *MMWR Morbid Mortal Week Rep* **58**, 421-426
3. Stevens-Lapsley, J. E., Balter, J. E., Wolfe, P., Eckhoff, D. G., and Kohrt, W. M. (2012) Early neuromuscular electrical stimulation to improve quadriceps muscle strength after total knee arthroplasty: a randomized controlled trial. *Phys Ther* **92**, 210-226

Research coordinator, who is an UVMMC employee in the Dept of Medicine, will screen surgical schedule for physicians in the Dept of Orthopaedics and Rehabilitation for patients that meet basic procedural eligibility (receiving a unilateral total knee arthroplasty procedure) and eligibility criteria (age, BMI, absence of exclusionary comorbid conditions, etc) to identify prospective participants. The coordinator will notify care providers in the Dept of Orthopedics and Rehabilitation of potentially eligible patients. An Ortho care provider will notify the patient that they may qualify for a research study and provide the patient with an IRB-approved trifold information pamphlet or provide a brief verbal summary of the study if contact is made by phone. The care provider will ask the patient if they would like to receive more information from research study staff.

Risks/Benefits:

Potential risks: Below we have highlighted those procedures/measurements that have anything greater than negligible risk to the volunteers' health for each phase of the study.


NMES intervention: NMES is a generally safe procedure, delivered in the proposed study by an FDA approved device. Although evidence is limited, some have suggested that NMES could increase the risk of DVT, which may have serious health consequences. However, several published reports show that NMES significantly reduces the risk of developing DVTs (2) and we will actively exclude any individual with a known coagulopathy. Because of the location of the stimulating electrodes (upper leg), the risk of NMES dislodging a DVT is likely minimal. We will also exclude any prospective volunteers that currently have an implanted cardiac defibrillator or pacemaker, as this is contraindicated for NMES use (2). Patients may experience some painful muscle contractions as they first adjust the stimulus to a tolerable level, this will be quickly mitigated by reducing the stimulation intensity. After treatment, muscles soreness may occur. The level of fatigue and/or soreness, however, will be similar to that which occurs following a standard exercise training session and should dissipate over time as the volunteer's muscles become accustomed to the electrically-stimulated contractions (ie, they become trained). In studies of the use of NMES in the post TKA population, our laboratories (including our co-I, [name], who has conducted NMES in NIH-funded RCTs; (3)) have never experienced an adverse event related to the use of NMES.

Leg movement with Biostamp sensors: Wearing the sensors causes little to no discomfort in most individuals, similar to wearing a Band-Aid. The BioStamp nPoint sensors are not intended for use on patients with known allergies or hypersensitivities to adhesives or hydro-gel. In absence of a known

allergy or hypersensitivity, it is possible the sensor and/or adhesive may still cause mild discomfort, skin irritation, redness, rash or contact dermatitis in some individuals. The BioStamp nPoint sensors are not intended for use on patients who have implanted pacemakers, defibrillators, or other active implantable devices. As volunteers with these implanted devices are already excluded from study, this risk is obviated. There is a small risk that a participant's electronic information could be accessed thereby affecting their confidentiality.

Benefits: The direct benefit of the research to volunteers is minimal. NMES may improve skeletal muscle structure or function and, in turn, improve physical functional capacity, as our collaborator's RCT demonstrated (3). Because of this, patients may experience improved physiological capacity, which could reduce disability post-surgery. If NMES is shown to have beneficial effects on skeletal muscle, further research and application of the technique to TKA recipients may assist in the development of more effective post-TKA care to mitigate long-term functional morbidity in these patients in the future, as well as provide compelling evidence to extend this intervention into other post-surgical populations to improve functional recovery.

References cited above:

1. Tarnopolsky, M. A., Pearce, E., Smith, K., and Lach, B. (2011) Suction-modified Bergström muscle biopsy technique: Experience with 13,500 procedures. *Muscle Nerve* **43**, 716-725
2. Houghton, P. E., Nussbaum, E. L., and Hoens, A. M. (2010) Electrophysical agents. Contraindications and precautions: an evidence-based approach to clinical decision making in physical therapy. *Physiother Can* **62**, 1-80
3. Stevens-Lapsley, J. E., Balter, J. E., Wolfe, P., Eckhoff, D. G., and Kohrt, W. M. (2012) Early neuromuscular electrical stimulation to improve quadriceps muscle strength after total knee arthroplasty: a randomized controlled trial. *Phys Ther* **92**, 210-226

Data Safety and Monitoring:

Our study is a clinical trial based on the recently-revised NIH definition (NOT-OD-15-015), but not a phase III clinical trial. Thus, pursuant to NIH regulations, we had originally established a formal Data Safety Monitoring Plan, which would provide additional oversights to further protect against risk to safety and confidentiality. The Clinical Trial Branch of the NIA has reviewed our protocol and made the determination that our study could be monitored by an outside Safety Officer through a standard DSMP format.

these studies, we have not incorporated "stoppage criteria" for the overall study. Instead, the Safety Officer will decide whether an individual participant should continue with the study following occurrence of any adverse events or unanticipated problems, taking into consideration what is in the best interest of each individual patient.

Adverse events will be reported by one of 3 mechanisms. First, the joint University of Vermont/University of Vermont Medical Center (UVMC) Committee for Human Subject Research Adverse Event Reporting Document. These reports will be forwarded to the office of the Committee for Human Research in the Medical Science (CHRMS) within 5 days of the event. Reporting any adverse events will be the responsibility of the PI. The CHRMS will make a determination as to whether additional reporting requirements are indicated. Second, the UVMC Patient Safety Reporting system (SAFE), which may be initiated by health care center staff or study personnel. These forms will be forwarded within 3 days to the PI, UVMC Risk Management Office, CHRMS and other appropriate agencies, as indicated by the nature of the report. Finally, the UVMC Medication/IV Event Report Form, with distribution and timing as noted above. This latter mechanism might be used with events related to blood sampling. Reviews of protocol specific adverse events will be performed no less than annually. Additionally, any adverse event that occurs will be forwarded to the PI for reporting to the Human Subject Research Protection Office within 1 week of occurrence. Of note, these protections against risk include both physical risks to the volunteers, as well as risks associated with any breach in confidentiality.

On an annual basis, Drs. [name], [name] and the Safety Officer will assess data being gathered and safety of volunteers to assess the pattern or frequency of events to identify occurrence of any event or problem that significantly alters the safety profile of the procedures being performed, unless occurrence of a serious adverse event or unanticipated problem necessitates re-evaluation of the expected risk of the study procedures at an earlier time point. Additionally, they will evaluate data collection and storage to ensure the confidentiality of data and quality. Each of these evaluations will be followed by reports of study progress and patient safety to the University of Vermont CHRMS via yearly progress reports and to the appropriate NIH program officer. The report will include information regarding study status and safety of volunteers (occurrence of AEs/SAEs. This report will also be forwarded to the NIH Program Officer for his review.

Withdrawal Procedures: Define the precise criteria for withdrawing subjects from the study. Include a description of study requirements for when a subject withdraws him or herself from the study (if applicable).

Volunteers will be withdrawn if the research team, clinician and/or safety officer feels that further participation in the study or performance of any procedure associated with this study would, in any way, put the volunteer at undue risk or not be in their best interest. Moreover, volunteers may be withdrawn if s/he fails to attend scheduled visits or do not comply with instructions from research staff.

Sources of Materials: Identify sources of research material obtained from individually identifiable human subjects in the form of specimens, records or data. Indicate whether the material or data will be obtained specifically for research purposes or whether use will be made of existing specimens, records or data.

An individual research record will be kept on each volunteer in compliance with HIPAA standards. This record will contain identifying data, demographic information and results from all clinical research measurements and evaluations. The results of all testing will be kept confidential. In addition, skeletal muscle tissue samples will be taken and will be used for measurement of muscle size, structure and function. All materials gathered in conjunction with the proposed studies will be used for research purposes only and will be available only to research personnel working on these studies, who have obtained proper training in human subjects research and privacy protection.

DRUG AND DEVICE INFORMATION

Drug (s)	 Not applicable
Device (s)	 Not applicable

Device name and indications

The interventional device used in this study: EMPI Continuum complete electrotherapy system has received FDA approval (501K: K093324) for retarding disuse-related atrophy, which we believe is one of the primary mechanisms whereby muscle adaptations evolve in TKA recipients in the early, post-surgical period. That is, muscle disuse secondary to pain, limited range of motion and muscle weakness

(the latter being due to neural inhibition caused by joint pain/swelling) causes skeletal muscle fiber atrophy and weakness and mitochondrial rarefaction and dysfunction.

Is it FDA approved:

Yes. It is approved to mitigate muscle atrophy/dysfunction associated with muscle disuse (501K: K093324) (see Appendix 3).

Risk assessment (non-significant/significant risk)

The device (and similar devices) has been used extensively in the orthopedic and neural rehabilitation settings by physical and occupational therapists and in numerous disease states (heart failure, chronic obstructive pulmonary disease, knee replacement) to improve muscle size and function in clinical trial settings. Thus, NMES is generally a safe modality, with a long safety record. Although evidence is limited, some have suggested that NMES could increase the risk of dislodging a deep vein thrombosis (DVT) because of the rhythmic muscle contractions induced by the electrical stimulation. However, several published reports show that NMES significantly reduces the risk of developing DVTs. In fact, the device we are using is FDA-approved for prevention of DVT of the calf muscles immediately following surgery, as it would function similar to intermittent pneumatic compression. Moreover, we will actively exclude any individual with a known coagulopathy or DVT. Because of the location of the stimulating electrodes (upper leg), the risk of NMES dislodging a DVT is likely minimal. There are also several case reports that NMES may be sensed by cardiac defibrillators as an arrhythmia, causing the device to discharge inappropriately. However, interference with ICDs mostly involved low frequency stimulation of the upper or lower back. In contrast, a more recent study has shown that higher frequency stimulation of the leg muscles does not cause electromagnetic interference with the device (1). Regardless, consistent with current clinical practice guidelines (2), we will exclude any volunteers that currently have an implanted cardiac defibrillator or pacemaker. Finally, during the first couple of NMES sessions, muscle soreness may occur, but this is comparable to what might occur with classical exercise training and dissipates over time.

Literature cited

1. Kamiya, K., Satoh, A., Niwano, S., Tanaka, S., Miida, K., Hamazaki, N., Maekawa, E., Matsuzawa, R., Nozaki, K., Masuda, T., and Ako, J. Safety of neuromuscular electrical stimulation in patients implanted with cardioverter defibrillators. *Journal of Electrocardiology* **49**, 99-101
2. Houghton, P. E., Nussbaum, E. L., and Hoens, A. M. (2010) Electophysical agents. Contraindications and precautions: an evidence-based approach to clinical decision making in physical therapy. *Physiother Can* **62**, 1-80

Inclusion of Minorities and Women:

Inclusion of Women

This study will include equal numbers of men and women.

Inclusion of Minorities

Every effort will be made to recruit minorities for the proposed studies. The contribution of minorities to the total population of Vermont is 3.2%, with a similar minority profile in Chittenden County (3.6%), where the University of Vermont (UVM) is located.

Inclusion of Children:

The proposed studies will not include children. The rationale for this decision is based on the fact that total knee replacement is confined to the adult/ older adult population.

Statistical Analytical Plan

Project Title:

Skeletal muscle atrophy and dysfunction following total knee arthroplasty

Version Date:

3-23-22

NCT number:

NCT03051984

**Principal
Investigator
(contact):**

[name]

Grant Sponsor:

NIA R01 AG050305

For Aim 1, using pre-surgery and 5 wk post-TKA assessments in the control group, we will assess the effect of TKA (pre- vs. 5 wk post-TKA) on muscle fiber size and function. Primary outcomes include: single muscle fiber CSA for MHC I and IIA fibers and tension and velocity for MHC I and IIA fibers, and IMF and SS mitochondrial content. We will use a general linear mixed model, with a random effect to account for observations clustered within patients (eg, single fiber CSA and function), with the model conceptualized as a multi-level analysis with single fiber values comprising level 1 variables and whole muscle or person-level covariates comprising level 2 variables (130). Covariates (eg, baseline value, etc.) can be included in the model as level 2 variables to determine if variation in any primary outcome is related to variability in these factors. Additionally, we can include sex in the model to examine whether the effects of TKA differ between men and women. In secondary analyses, we will examine whether changes in muscle fiber size or functional mediate changes in whole muscle and body function using mediation analysis, if effects of TKA are noted in the latter. Such analyses seeks to determine whether the effect of an independent variable or intervention (TKA) on some outcome variable (whole muscle/body function) can be transmitted through a third variable, referred to as a mediator (single fiber CSA or function). Variables with multiple observations per subject will be collapsed into a single mean value.

For Aim 2, pre- and 5 wk post-surgery data will be compared between volunteers randomized to NMES and control interventions. Our primary analysis will assess treatment effects (group X time interaction) on muscle structural and functional variables. Primary outcomes are identical to Aim 1 and will be similarly evaluated using a general linear mixed model, as described above, with group (NMES vs. control) and time (pre vs. 5wks post-TKA) as between- and within-subject factors, respectively. Potential confounding factors will be compared between groups and factors that differ can be included into the model as level 2 covariates. We assume that dropouts will be random, but will examine whether they differ from volunteers completing the study. Moreover, we can conduct sensitivity analysis on dropouts, assuming the most and least conservative responses, to assess their impact on study outcomes. Additionally, we can include sex as an additional effect in these models to determine if NMES effects differ by sex. In secondary analyses, we will also examine the effect of treatment on whole muscle/body functional measures. If there are effects of NMES to maintain whole muscle/body functionality at 5 weeks, we will examine whether changes in single fiber structural or functional outcomes partially or completely mediate whole muscle/body functional improvements with NMES using mediation analysis.

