Hypothesis: TKA will impair whole body and muscle function, in part, through reductions in skeletal muscle fiber size, with preferential atrophy in MHC II sub-types, reduced single fiber tension (force/CSA) and velocity and decreased mitochondrial content and function.

Aim 2: Define the utility of NMES to prevent early, postsurgical skeletal muscle structural and functional adaptations to TKA.

Hypothesis: NMES will lessen TKA-induced muscle fiber atrophy and contractile dysfunction and preserve or increase mitochondrial content and respiration while lessening mitochondrial ROS production.

METHODS AND PROCEDURES

We will use a randomized, controlled design, in which older adult patients with knee OA being evaluated for TKA will be recruited and undergo baseline evaluations (Pre-surgery Testing) prior to surgery. Patients will then be randomized (1:1) to a 5 week intervention of NMES or control (n=32/group, expecting 25% attrition rate to arrive at n=24/group) using a covariate-adaptive approach, which will incorporate age, BMI, sex and surgeon into the randomization scheme. After completing the intervention, they will be re-tested at 5 weeks (5 wk Post-surgery Testing) following surgery. Volunteers can opt into an optional 2 week follow-up testing period. Primary outcomes will be tested at the 5 week evaluation, with 2 wk testing including assessment of ancillary mechanistic hypotheses. Assessment of physical activity by accelerometry (5 d each throughout the 5 week post-surgical period) will monitor variation in physical activity between groups. Each phase of the protocol is described below.

Pre-surgery testing will include assessments of whole muscle size and function, accelerometry to assess habitual weight-bearing activity level, single muscle fiber size and mechanical function and mitochondrial content and function. Detailed descriptions of these assessments are provided below.

Treatment intervention Volunteers will be randomized to NMES or control groups for the 5 weeks following TKA surgery (described below in detail).

5 wk Post-surgery testing will include measurements identical to Baseline Testing, with post-training biopsies performed ≥ 3 d following strength testing/NMES to eliminate any residual effects, per our usual protocol in our past IRB-approved training studies in other clinical populations (heart failure, end-stage knee osteoarthritis).

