2 wk Post-surgery testing (optional) will consist of a skeletal muscle biopsy to assess single muscle fiber size, mitochondrial content and function and anabolic catabolic signaling pathways via standard biochemical/immunolabeling techniques.

6 month Post-surgery testing will include assessments of whole muscle size and function and whole body functional measures to provide data on whether hypothesized preservation in single muscle fiber size/function with NMES will relate to longer-term improvements in whole muscle size/function and whole body functionality.

Procedures:

All of the procedures and interventions on volunteers recruited for these studies are carried out solely for research purposes, as none are part of standard therapy in TKA patients. We will describe procedures that will be performed for each of the Aims.

Aim 1

Primary outcomes, which will be assessed at baseline and 5 wk post-intervention, include: skeletal muscle fiber cross-sectional area (CSA) and function, mitochondrial content, morphology and function and weight-bearing activity. Secondary outcomes include: whole muscle size/function and accelerometry. Procedures that will be performed on volunteers to obtain these primary and secondary outcome measures are described below.

Pre-surgery testing

Percutaneous skeletal muscle biopsy of the vastus lateralis (VL) will be performed on the leg scheduled to undergo TKA, per procedures used by our research group in a range of patient populations, including knee OA patients (1, 2). Tissue will be proportioned for mechanical (single fiber function), immunohistochemical (IHC), mitochondrial functional (oxygen consumption rate and hydrogen peroxide production) and electron microscopy (EM) measurements, with remaining tissue frozen in liquid N₂. The VL was chosen because of its importance in determining functional disability (3) and its structural and functional adaptations to TKA (4). The following measures will be assessed from muscle tissue.

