Questionnaires will consist of the Western Ontario and McMaster Universities Arthritis Index (WOMAC) and Medical Outcomes Short Form (SF-36; Appendix 1) form to assess the symptom severity of the volunteer's knee OA, as well as their functional status and quality of life to be used as basic data to characterize the cohort so that, upon publication, readers can assess the external validity of our cohort.

NMES

NMES will be conducted on the quadriceps of the operative leg using a portable stimulation device (Empi Continuum; DJO Global), starting within 48-72 hrs of surgery, as described by us (21), and used in our preliminary studies at UVM (CHRMS 12-184). Briefly, the operative leg will be immobilized on a support board at a neutral angle (30°) or using a knee positioning bolster and ankle weight, with electrodes affixed to the anterior surface of the thigh. Symmetrical, biphasic pulses (400 µs duration at 50 Hz) will be used, with a duty cycle of 25% (10 s on, 30 s off), with patient-selected stimulation intensity to cause visible contractions below pain threshold. NMES sessions will occur 5 d/week, twice daily for 45 min (5 min warm-up) for 5 wks. Our prior trial (21) had excellent compliance, with 91 ± 2% of sessions completed at 5 weeks post-TKA, with compliance not related to age (P>0.5) or number of comorbidities (P>0.5). Studies utilizing muscle biopsies have yielded a similarly high compliance with

NMES (93 ±4%). Thus, we have assumed an attrition rate of 10% due to non-compliance. To track the NMES dose, volunteers will self-report device intensity (mA), as well as knee pain (see Appendix 2), with reports reviewed weekly by the study coordinator. Compliance will be confirmed using the compliance monitoring feature built-in to the device software and we will measure NMES dose (% pre-surgery MVIC) directly at 5 weeks post-TKA, as described (22).

Control

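### Aim 1's control-only pre/post analysis is valid, but a joint model with one common pre-surgery mean would also use the NMES arm's pre-randomisation biopsies and give a modest gain in precision

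*SAP*

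**What the plan says.** The Aim 1 paragraph of the SAP defines the data for the TKA effect: "using pre-surgery and 5 wk post-TKA assessments in the control group, we will assess the effect of TKA". On the model it says: "We will use a general linear mixed model, with a random effect to account for observations clustered within patients". The primary outcomes are fibre CSA, tension and velocity, each in MHC I and IIA fibres, plus IMF and SS mitochondrial content, which makes eight.

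The Protocol (Methods and Procedures) fixes the order of events. Patients "will be recruited and undergo baseline evaluations (Pre-surgery Testing) prior to surgery. Patients will then be randomized (1:1" to NMES or control. The biopsy belongs to that pre-surgery testing (Procedures, Aim 1): "Percutaneous skeletal muscle biopsy of the vastus lateralis (VL) will be performed on the leg scheduled to undergo TKA". The planned numbers are "n=32/group, expecting 25% attrition rate to arrive at n=24/group".

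The NMES arm's pre-surgery values are used in Aim 2: "For Aim 2, pre- and 5 wk post-surgery data will be compared between volunteers randomized to NMES and control interventions". The Aim 2 model has group, time and their interaction. Neither document states that the arms share one pre-surgery mean, or that NMES-arm baselines inform Aim 1.

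**The concern.** Both arms' pre-surgery biopsies sample one population: they are taken before allocation, and NMES cannot have affected them. Only the NMES arm's 5 wk values must be kept out of an estimate of what TKA does without NMES. Aim 1 nevertheless uses the controls' baselines alone.

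The Aim 2 model as described does not change this. With a full group-by-time structure and no common-baseline constraint, its control-arm time contrast rests on the controls and takes essentially nothing from NMES-arm baselines.

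What is at stake is the width of the Aim 1 intervals. That aim rests on about 24 biopsy pairs for eight primary outcomes, obtained by an invasive procedure. Tissue already collected could narrow the intervals without further visits.

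**Working it through.** **Inputs from the documents.** 32 randomised per arm, 25% attrition, 24 completers per arm (Protocol, Methods and Procedures). The plan's own figure reproduces: 24/(1 − 0.25) = 32. The NMES section adds "Thus, we have assumed an attrition rate of 10% due to non-compliance" without saying how this relates to the 25%; it is not used here. No alpha, power, SD or effect size is given, so the 24 cannot be rederived.

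**Assumed inputs.** Pre-post correlation r of patient means, 0 to 0.9. Ratio k of 5 wk SD to pre-surgery SD: 0.7, 1 or 1.3. Dropout at random.

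**Formula.** Set the pre-surgery SD to 1. With n control pairs and N baselines sharing one mean, the control-arm change has variance

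V(N) = k²(1 − r²)/n + (1 − rk)²/N.

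With N = n this is the ordinary paired result, (1 + k² − 2rk)/n. Extra baselines shrink only the second term.

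**Equal SDs (k = 1), n = 24.** Two comparisons matter:
- A: 24 control pairs only, against the same pairs plus 24 NMES baselines (N from 24 to 48). The variance ratio simplifies to (3 + r)/4.
- B: the mixed model already keeps all 32 control baselines, and 32 NMES baselines are added (N from 32 to 64).

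| r | A: variance ratio | A: fall in SE | B: variance ratio | B: fall in SE |
|---|---|---|---|---|
| 0 | 0.750 | 13.4% | 0.786 | 11.4% |
| 0.3 | 0.825 | 9.2% | 0.856 | 7.5% |
| 0.5 | 0.875 | 6.5% | 0.900 | 5.1% |
| 0.7 | 0.925 | 3.8% | 0.942 | 3.0% |
| 0.8 | 0.950 | 2.5% | 0.962 | 1.9% |

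Example, B at r = 0.5: (0.75/24 + 0.25/64)/(0.75/24 + 0.25/32) = 0.03516/0.03906 = 0.900, and 1 − √0.900 = 5.1%. In pairs, A at r = 0.5 is worth 24/0.875 = 27.4 instead of 24; at r = 0.8 it is 24/0.950 = 25.3.

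**Unequal SDs, r from 0 to 0.9.**
- k = 0.7: the SE falls by 13.7 to 18.5% under A and 11.6 to 16.5% under B. Example, A at r = 0.5: (0.49 × 0.75 + 0.65²/2)/(1 + 0.49 − 0.70) = 0.579/0.79 = 0.733, and 1 − √0.733 = 14.4%.
- k = 1.3: the SE falls by 0.1 to 9.8% under A. The gain nearly vanishes at r = 0.7 to 0.8, where rk is close to 1.

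A ratio below 1 is plausible if spread shrinks with the mean, since the Protocol's background reports contractility deficits of about 30 to 50% after TKA. That link is itself an assumption.

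**Cost of estimating the slope.** The formula treats the pre-post slope as known. In simulation, with the slope estimated from the 24 control pairs, the equal-SD ratio under A is 0.89 rather than 0.875 at r = 0.5, and 0.975 rather than 0.950 at r = 0.8. At k = 0.7 it stays at about 0.68 to 0.76. At k = 1.3 with r = 0.7 to 0.8 it reaches about 1.02, a 2% loss in variance.

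**Pooling without a model.** Subtracting a simple mean of 48 baselines from the controls' 5 wk mean gives a ratio of (1.5 − r)/(2(1 − r)). This is 1.00 at r = 0.5 and 1.75 at r = 0.8, so the pairing must be kept.

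**The case against.** The strongest reply is that nothing is wrong. A within-patient contrast in patients who did not receive NMES answers the Aim 1 question directly, and no bias or inflated error rate follows from it. The documents set no precision target that it would miss. All of that stands.

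Three stronger readings are tempting, and the documents support none of them:

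- A reader might infer that the NMES-arm biopsies are wasted. They are absent from the Aim 1 contrast only; Aim 2 uses them for the same primary outcomes.
- A reader might infer that Aim 1 also drops the baselines of controls who have no 5 wk biopsy, and so compare 64 baselines with 24. That would give variance reductions of about 31/22/16/9% at r = 0/0.3/0.5/0.7. The SAP states no restriction to completers, and a mixed model can keep those patients. Comparison B is the fair one when all baselines are counted.
- A reader might infer that the gain is free. It needs a prespecified common-baseline constraint and an adequate pre-post covariance with fibres nested in patients. In an unfavourable case it costs about 2% in variance.

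The objection fails only in treating the choice as indifferent. Randomisation after baseline testing justifies the constraint, and over most of the range examined the joint model is the more precise.

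**Conclusion.** The point holds as a suggestion about efficiency. The control-only analysis is valid, and the joint model would usually be somewhat better. With equal SDs the fall in standard error is about 13/9/6.5/4/2.5% at correlations 0/0.3/0.5/0.7/0.8, or about 11/7.5/5/3/2% if all 32 control baselines are already in the model. Across the two comparisons it is about 12 to 18% at an SD ratio of 0.7; it is near zero at a ratio of 1.3 with high correlation. These figures rest on assumed correlations and SD ratios, work at the level of patient means, and assume random dropout.

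It should not be read as showing that Aim 1 is biased or underpowered. Nor would the change strengthen causal attribution: Aim 1 remains a before-after comparison with no group that forgoes surgery, and extra baselines inform the untreated 5 wk mean only through the pre-post correlation.

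**What to change.** Amend the Aim 1 paragraph of the SAP to specify:

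1. One mixed model on all randomised patients, with a single pre-surgery mean common to both arms and separate 5 wk means for control and NMES.
2. Patient-level pre and post variances and the pre-post covariance left free, with fibres nested within patient and visit. State whether these parameters are shared by the arms or arm-specific.
3. The control-arm time contrast from this model as the Aim 1 effect of TKA.
4. The control-only pre/post analysis as a sensitivity analysis.

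The choice should be fixed before outcome data are examined, because picking between the two data sets afterwards would be open to challenge. The cost is SAP wording, slightly more modelling and reliance on the common-baseline constraint. No new tissue or visits are needed.
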